### **Recruitment**

Recruitment will occur through medical referrals from primary physicians of several public and private hospitals in the Algarve region. Additionally, the project will be presented at breast cancer-themed congresses and events, and digital flyers with information about the study will be made to assist in disseminating the project and the recruitment process. A research team member will then contact patients referred by the doctors to receive detailed information about the study. Optionally, patients can call the research team directly or contact them through email if they prefer. After confirming eligibility criteria and interest in participating in the study, patients will be asked to attend an initial session where more information will be given, and the informed consent will be signed. During that session, participants will be told they are not obliged to participate in the study and may decide to leave the project. Consent for data collection or sharing will also be obtained.

### **Assignment of interventions**

#### **Allocation**

##### **Sequence generation**

After signing the informed consent form, participants will be given a number, randomly generated through Excel and emailed by a non-interventionist team member, which will be their participant number throughout the study. Participants will be instructed not to reveal their number to the research team or the other participants and to keep it with them until the end of the study. After all baseline assessments, participants will be randomly assigned to either the intervention or control arm through an online program (<https://www.graphpad.com/quickcalcs/randomize1/>). If recruitment takes longer than expected, adjustments in allocation may be made.

### **Allocation concealment mechanism**

Participants and research team members will be unaware of group allocation during recruitment and baseline assessments. A non-interventionist research team member will fill in the measurements' results during the field tests. This team member will be the only person, besides the participant, who will know the participant's number. The participants will identify the questionnaires with their numbers.

### **Implementation**

After all questionnaires have been received, the random allocation will be performed. The non-interventionist team member will email all participants the numbers allocated in each group (intervention or control).

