### **Strategies to improve adherence**

Before implementing this study, a survey and focus-group-based study will be performed to adjust the exercise program to the preferences, perceived barriers, and facilitators of women with a breast cancer diagnosis, considering the environmental and cultural context from where the intervention will be conducted. The supervising professional will monitor adherence to the supervised sessions through presence registration. This study will also consider the participants' adherence to the control group. To attempt dropout minimization, we will have an active control group.

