### **Blinding (masking)**

Participants will be told they are part of an exercise intervention without any mention of a control group. The healthcare professionals responsible for the chemotherapy prescription and administration and registering all clinical information will be blinded to the participants' groups. None of the research team members will know the number of participants, so data analysis will be performed in a blinded setting. The exercise professional conducting the assessments will be blinded to the participant's number but not to which group the participant belongs. If, at any given moment, a participant reveals her number to a research team member, all posterior data from that participant will be disregarded. If a participant decides to leave the study or must abandon it due to health complications, the team member with the number information will be informed, and all further data will be disregarded from the analysis.

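### The e-mailed list of numbers by group conflicts with the plan not to mention a control group, and weakens participants' partial masking after baseline

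*Protocol*

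**What the plan says.** Four adjoining sections of the protocol bear on this.

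- **Sequence generation.** After consent, "participants will be given a number, randomly generated through Excel and emailed by a non-interventionist team member". The woman is asked not to disclose it to the research team or to other participants, and "to keep it with them until the end of the study".
- **Allocation concealment mechanism.** The period of unawareness is stated: "Participants and research team members will be unaware of group allocation during recruitment and baseline assessments".
- **Implementation.** The timing is given as "After all questionnaires have been received, the random allocation will be performed". A team member outside the intervention then "will email all participants the numbers allocated in each group (intervention or control", which is the step at issue here.
- **Blinding (masking).** This section opens with the statement that "Participants will be told they are part of an exercise intervention without any mention of a control group". That same section states that the healthcare staff who prescribe and give chemotherapy are blinded, with those "registering all clinical information will be blinded to the" participants' groups. It bases the blinded data analysis on the team not knowing the numbers. It also says that the professional who conducts the assessments does know the group.

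No section says that the allocation e-mail uses neutral labels, goes out individually, or names only the recipient's own sessions.

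**The concern.** Participants in an exercise trial cannot be blinded to what they do in their sessions. Because the control arm is active, with supervised sessions of its own, the protocol can aim for something narrower: a woman need not know that her programme is regarded as the comparator. The allocation e-mail, as described, gives that away.

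At stake are the outcomes that a participant's expectations can move. QLQ-C30, QLQ-BR45 and IPAQ-SF are self-completed online. The six-minute walk, handgrip, arm curl and sit-to-stand tests depend on effort. Since the assessor of the field tests already knows the group, the participant's own lack of awareness is one of the few protections left for them. Control women are also free to be active on their own account, so knowing the label could change behaviour in either direction. These outcomes carry Hypotheses 2 and 3.

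**Working it through.** No sample size, effect size or error rate enters this point, and the protocol gives no figure to reproduce. The check is a comparison of texts.

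1. **Does each woman know her number?** Yes. Sequence generation has it e-mailed to her and kept to the end of the study.
2. **What does the allocation e-mail contain?** Under Implementation, the numbers belonging to each group, sent to all participants.
3. **What follows from 1 and 2?** She finds her number in one of two sets. She learns that there are two groups and which one holds her number. She does not learn other women's groups by name, because the numbers are meant to be private.
4. **Does this depend on the labels?** Only in part.
   - Labels used literally: a control woman learns that she is a control.
   - Neutral labels: she still learns that there is a second group and which set is hers, but not which set is the comparator.
   - On either reading the message discloses a comparison group, which the opening sentence of Blinding (masking) withholds.
5. **When does it happen?** After the baseline assessments and questionnaires, so before T1, T2 and T3.
6. **Which safeguards are touched?**

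| Safeguard | What it rests on | Effect of the e-mail |
|---|---|---|
| Concealment during recruitment and baseline | Allocation comes afterwards | None |
| Participants not told of a control group | What participants are told | Weakened for every participant |
| Clinicians blinded to group | Clinicians not being informed | Not directly undone |
| Blinded data analysis | Team not knowing the numbers | Not directly undone |
| Field assessor | Already aware of group | No change |

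**The case against.** The strongest reply has four parts.

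- **The wording of the e-mail is unknown.** The parenthesis naming the two groups may be an explanation for readers of the protocol and not text for participants. This stands, and it means nobody can say for certain that control women will see the word control. It does not remove the conflict, because a list divided by group reveals a second group under any labels.
- **The two sections may refer to different times.** Allocation concealment mechanism limits unawareness to recruitment and baseline, and the sentence under Blinding (masking) carries no date. It could describe only what is said at enrolment. A reader might infer that the two steps cannot both be carried out, and on this reading they can. The text remains unclear, because a statement under the heading of blinding is naturally taken to cover the trial period. The consent pages are not available to settle it.
- **The arms look different anyway.** One offers two weekly 60-minute sessions of resistance and aerobic work and a pedometer. The other offers one weekly 30-minute session of breathing, stretching, relaxation and meditation. Assessments take place in small groups, where women may compare notes. Some would infer their arm without any e-mail. This stands, so the e-mail cannot be charged with the whole loss of masking.
- **The primary outcome is protected separately.** Relative dose intensity comes from medical records kept by staff who are stated to be blinded. This also stands. A woman could tell her clinicians her group, since she is asked to keep only her number private, but that route is open through session content too.

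A reader might also infer that the label would raise dropout in the control arm, because the protocol says "To attempt dropout minimization, we will have an active control group". The documents give no figure for such an effect and do not show that one exists.

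**Conclusion.** The inconsistency between Implementation and Blinding (masking) is real and should be corrected before any allocation e-mail is sent, because the disclosure cannot be taken back. As described, the e-mail shows all participants, after baseline, that there is a comparison group and which group they are in. If the labels are literal, it tells control women that they are controls. This weakens a partial protection for self-reported and effort-dependent secondary outcomes whose field assessor is already unblinded.

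The reach is every participant. The size of any bias, and its direction, cannot be derived from the documents. The conclusion assumes that the e-mail is sent as Implementation describes and that the sentence on not mentioning a control group is meant to hold beyond enrolment.

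It would be too much to conclude that the trial has no masking. Concealment up to baseline, clinician blinding and the number-based analysis rest on other arrangements, and participant masking was only ever partial.

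**What to change.** Keep the allocation point as planned, after the baseline questionnaires are in. In place of one message with the list:

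- send each woman an individual message with only her own programme, under a neutral name such as Programme A or Programme B, and its schedule;
- do not circulate the numbers by group to participants;
- reword Implementation to describe this;
- reword Blinding (masking) to say that women are told they will be assigned at random to one of two supervised programmes, with neither presented to them as the control;
- check that the consent information says the same.

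The last two changes narrow what the protocol promises. Women will know that there are two programmes, but not which is the comparator. That is a protection the trial can deliver, subject to what women infer from session content.

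The cost is individual instead of bulk e-mails and a few sentences of protocol text, plus the consent wording if it differs. Sample size, timing of allocation, session content and analysis do not change.

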### **Blinding (masking)**

Participants will be told they are part of an exercise intervention without any mention of a control group. The healthcare professionals responsible for the chemotherapy prescription and administration and registering all clinical information will be blinded to the participants' groups. None of the research team members will know the number of participants, so data analysis will be performed in a blinded setting. The exercise professional conducting the assessments will be blinded to the participant's number but not to which group the participant belongs. If, at any given moment, a participant reveals her number to a research team member, all posterior data from that participant will be disregarded. If a participant decides to leave the study or must abandon it due to health complications, the team member with the number information will be informed, and all further data will be disregarded from the analysis.

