## **Trial design**

This study will be a 2-arm pragmatic and superiority randomized controlled trial with an intervention and an active control group, with a 1:1 allocation ratio. It will comprise a structured, supervised, home-based combined exercise intervention that will start 1-2 weeks after chemotherapy treatments begin and continue until 3-4 weeks post-treatment. Additionally, a 3-month follow-up will be performed. This protocol followed the Spirit guidelines.

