### **Interventions**

**Combined home-based exercise group.** Participants in this group will exercise throughout their chemotherapy treatments, starting within 1-2 weeks of its start and ending within 3-4 weeks post-treatment completion .

The exercise intervention will be led by qualified exercise professionals, comprising two weekly 60-minute online exercise group sessions with a 5-minute warm-

up, a 30-minute resistance training, and a 20-minute aerobic exercise component, finishing with a 5-minute cooldown . The warm-up will be composed of mobility and activation movements, such as cat-camels, butterfly chest stretch, overhead reach, floor angels, spine twist in sitting and alternated all fours position, doorway chest stretch, wall slides, scissors, pointer, and single leg stances. The resistance training component will consist of 9 different exercises, performed either with body weight or free weights, completing 2-3 sets of 10-15 repetitions, and will involve movements such as chair sit-to-stand, multi-directional lunges, calf, and toe raises, double-arm and one-arm rows, push-ups, glute bridges, clams, chest press, multi-directional shoulder raises, leg curls, and abdominal exercises (i.e., crunches, leg raises, crisscross) . The aerobic component will consist of low-impact dance exercises, moving large muscle groups to increase heart rate, involving marching, side steps, knee raises, leg curls, multi-directional arm movements, and dance movements . The cooldown will consist of breathing exercises and light stretches. Every exercise professional will follow a written protocol to ensure consistency in the intervention program's application .

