Before the beginning of the exercise program, participants will receive an education session on how to use Borg's Perceived Rate of Exertion Scale (RPE) to monitor their effort during aerobic and resistance training and tips on when they may increase the exercise intensity . During the training sessions, participants in the intervention group will be asked to choose their preferred load to execute each exercise in the resistance component, told to perform the aerobic exercises at their preferred speed, and informed that they can stop exercising whenever they need to rest. The exercise professional may suggest increasing loads in specific exercises, but these increases will not be imposed on the participants. Attendance to the sessions in the intervention and control groups will be registered. Additionally, women in this group will be encouraged to perform brisk walking at their preferred intensity and receive a pedometer to increase walking motivation .

**Control group.** Women randomized to the control group will receive weekly 30-minute supervised sessions with breathing, stretching, relaxation exercises, and meditation during the intervention period . Women in this group will not be forbidden to perform PA but will not receive any incentives or advice from the supervising exercise professional.

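### Women are to be told of an exercise intervention with no mention of a control group, yet the allocation e-mail names one, so the stated participant masking fails and disclosure of the random comparison at consent is left open

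*Protocol*

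**What the plan says.** Under Blinding (masking), the Protocol sets what women hear about the study: "Participants will be told they are part of an exercise intervention without any mention of a control group". The sentence makes no distinction by arm.

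The Trial design section describes a superiority trial "with an intervention and an active control group, with a 1:1 allocation ratio". The Interventions section gives the exercise arm a programme "comprising two weekly 60-minute online exercise group sessions", with walking encouragement and a pedometer as well. The control arm receives "weekly 30-minute supervised sessions with breathing, stretching, relaxation exercises, and meditation during the intervention period", with no incentive or advice to be active.

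On timing, the Recruitment section says "patients will be asked to attend an initial session where more information will be given, and the informed consent will be signed". Randomisation comes later: "After all baseline assessments, participants will be randomly assigned to either the intervention or control arm through an online program" (Sequence generation). The Allocation concealment section adds: "Participants and research team members will be unaware of group allocation during recruitment and baseline assessments". Once the allocation is made, the Implementation section says: "The non-interventionist team member will email all participants the numbers allocated in each group (intervention or control").

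**The concern.** Two things are at stake.

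The first is the consent information. The one sentence that fixes what women are told describes the exercise arm much better than the control arm, and it deliberately leaves out the comparator. Recruitment and Consent or assent mention detailed information, voluntary participation and the right to withdraw. Neither mentions chance assignment or a second programme.

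The second is the masking claim. If women discover after consent that there is a control group and that they are in it, an expectation of exercise has been raised in both arms and disappointed mainly in one. Controls may then attend less, leave more often, or answer the activity (IPAQ-SF) and quality-of-life (EORTC) questionnaires differently. An arm difference in those outcomes would be partly a reaction to the allocation.

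**Working it through.** The Protocol gives no figure to reproduce here. The check is the order of events and whether the sections are compatible.

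**1. Order of events.** Consent at the initial session (Recruitment; Consent or assent); baseline assessments; randomisation (Sequence generation), once all questionnaires are in (Implementation); then the e-mail listing numbers by group (Implementation). If the Blinding sentence is followed, consent is given with no mention of the control group.

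**2. What the e-mail reveals.** Sequence generation gives each woman a participant number to keep until the study ends. Allocation concealment confirms that she and one team member know it. A list of numbers under the names intervention and control therefore tells her (a) that a control group exists and (b) whether she is in it.

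**3. Compatibility.** The Blinding section requires that no control group be mentioned. The Implementation section, read literally, mentions it to everyone. Both cannot be carried out. Non-disclosure would cover consent and baseline and end at allocation, before the sessions it was meant to protect.

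**4. How different the arms are.** Exercise: 2 × 60 = 120 supervised minutes a week. Control: 1 × 30 = 30 minutes a week. That is a ratio of 120/30 = 4, with different content. A woman expecting an exercise programme would notice.

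**5. How many women.** The Sample size section gives 98 and the Abstract gives 122. At 1:1, controls number 98/2 = 49 to 122/2 = 61.

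**6. Which results are exposed.**

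| Result | Exposure |
|---|---|
| Baseline questionnaires | Not affected by the allocation, because they precede it |
| Later IPAQ-SF and EORTC scores | Direct: self-reported by women who know their arm |
| Accelerometer activity | Recording is objective, though behaviour can change |
| RDI | Smaller direct route: taken from medical records, with prescribing and recording staff stated to be blinded |

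**7. How the plan handles those who react.** Data after a woman leaves are disregarded (Blinding). Low attenders and women who miss assessments are excluded (Plans to promote retention). Missing values are carried forward (Statistical methods). If attendance or dropout differs by arm, these rules bring that difference into the comparison. This is also the indirect route by which RDI could be affected.

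**The case against.** The strongest reply is that the consent form is not shown, and that avoiding the term control group is not the same as hiding the comparison. Women could be told of random assignment to two formats without that label, and the Recruitment section promises detailed information. This stands in part: ignorance of the randomisation is a strong inference from the Blinding sentence, not something the Protocol states.

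Several stronger readings are tempting but unsupported:

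- **That women are told no control group exists.** The text withholds mention; it does not deny.
- **That the statement is false for controls.** Their sessions include stretching and breathing exercises and are led by an exercise professional. Misleading is fair; untrue is not established.
- **That dropout will be unequal by a given amount.** The Protocol gives one overall figure, 20%, and no split by arm. It also says that the active control is there to limit dropout.
- **That controls are free to take up exercise programmes.** The Concomitant care section asks all participants not to join other programmes. For controls it leaves open activities such as brisk walking.
- **That the data become unusable.** Nothing in the document supports this.

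It can also be argued that fuller disclosure may itself increase disappointment or contamination. This carries little weight, because the plan as written already reveals the control arm, only after consent.

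**Conclusion.** The point holds in a limited form. The Blinding and Implementation sections contradict each other, and participants are not masked to the existence of a control group or to their own membership of it. This rests on a literal reading of the e-mail sentence and on each woman knowing her number, which the Protocol states. Separately, the Protocol fixes participant information that omits the control group and nowhere says that chance assignment is disclosed. Whether the consent form makes this good cannot be judged here.

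The consent question concerns every participant, and the disappointed expectation concerns mainly the 49 to 61 controls. The consequence is a plausible bias by arm in self-reported secondary outcomes and in who remains in the analysis. The document offers no basis for sizing it. The primary outcome is less exposed. The change should be made, but it is a correction of wording and of a masking claim, not a reason to doubt the whole design.

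**What to change.** - **Recruitment, Blinding, Consent or assent, and the consent text:** tell every woman that chance will assign her to one of two supervised programmes. Describe both in neutral terms (aerobic and strength exercise; breathing, stretching and relaxation). Do not say which is the comparator or which is expected to do better.
- **Implementation:** replace the names intervention and control in the allocation e-mail with neutral programme labels. This must accompany the first change; on its own it would leave the consent question open.
- **Blinding:** replace the present sentence with a statement that participants are not told the study hypothesis.

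The cost is new wording for the information session, consent form and e-mail, plus submission to the ethics committees, which the Protocol amendments section already requires. Sample size, assessments and analysis are unchanged. A small downside is that controls will know that the exercise programme exists, so contamination or disappointment may rise somewhat. The existing request not to join other programmes limits this, and the accelerometer will record changes in activity.

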### **Authors' contributions**

[name] conceived the project and wrote the manuscript. [name] revised and edited the manuscript and will randomly assign participants' numbers and random allocation. [name] and [name] assisted in project refinement and revised and edited the manuscript. Also, the former authors will supervise the entire trial.

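### The claim of a blinded analysis rests on hiding participants' ID numbers, which one team member knows and which would not hide the arm

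*Protocol*

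**What the plan says.** The Protocol's Blinding (masking) section states "None of the research team members will know the number of participants, so data analysis will be performed in a blinded setting". The word *so* makes the first half the reason for the second. The surrounding text shows that the number meant is each woman's ID, not a headcount.

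Other sections describe who holds that ID:

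- Sequence generation: the ID is "randomly generated through Excel and emailed by a non-interventionist team member".
- Allocation concealment mechanism: "A non-interventionist research team member will fill in the measurements' results during the field tests", and "This team member will be the only person, besides the participant, who will know the participant's number". The same section limits the team's ignorance of allocation to recruitment and baseline.
- Implementation: after the allocation is made, "The non-interventionist team member will email all participants the numbers allocated in each group".
- Plans to promote retention: the non-interventionist member converts the attendance register to IDs for the adherence analysis.
- Authors' contributions: one author "revised and edited the manuscript and will randomly assign" both the participant numbers and the allocation.
- Blinding (masking), further on: it refers to a team member who holds the ID information. It also says that the assessor does not know the ID but does know the group.

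The Protocol does not say who analyses the data, or whether that person sees labelled arms.

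**The concern.** The sentence gives a reason and a conclusion, and both have a problem. The reason is untrue as written, because a member of the research team does know the IDs. The conclusion would not follow even if the reason were true, because an ID protects identity and leaves the arm label untouched.

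What is at stake is the protection that a blinded analysis is meant to give. Statistical methods lists covariates only by example and lets normality checks trigger a change to non-parametric tests. Plans to promote retention drops low attenders and women who miss assessments, while Statistical methods promises an intention-to-treat analysis of everyone alongside a per-protocol one, so which exclusions govern which result is still a decision. If such choices are made by someone who can see the arms, they can be influenced by the results, even without intent. A report that repeats the Protocol's sentence would claim a safeguard that the described procedure does not supply.

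**Working it through.** The claim rests on no figure, so the check is a comparison of sections, plus one short calculation on attendance.

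**1. The premise.** Blinding (masking) says that no team member knows the IDs. Allocation concealment mechanism says that one does, and places that person within the research team. Plans to promote retention gives the role a task that cannot be done without the IDs, and the end of Blinding (masking) acknowledges that a holder exists. The universal statement is therefore false within the same document.

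**2. What else the holder has.** Sequence generation has a non-interventionist member issue the IDs. Allocation concealment mechanism says only one such member knows them. Implementation has that role send out the IDs by group, so the sender has an ID-to-arm list. Authors' contributions has one author assign both IDs and allocation. Read together, the ID holder appears also to hold the ID-to-arm list. This is an inference: Implementation does not say who runs the randomisation.

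**3. The inference to blinding.** There are two links: woman to ID, and ID to arm. The Protocol conceals the first. Data management stores the data under the ID, and any between-group comparison needs the second link as a variable in the dataset. Concealing the first link does nothing to the second. An analyst may not know who participant 37 (an arbitrary example) is and still see that 37 is in the intervention group. No section says that the group variable is coded or withheld.

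**4. Attendance as a second route to the arm.** Interventions gives two sessions a week in the intervention arm and one a week in the control arm. Over the same *w* programme weeks:

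- scheduled sessions: 2 × *w* = 2*w* (intervention) and 1 × *w* = *w* (control);
- attended sessions among women meeting the 50% per-protocol threshold: from 0.5 × 2*w* = *w* up to 2*w* (intervention), and from 0.5 × *w* = 0.5*w* up to *w* (control).

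The two ranges meet only at *w*. Raw counts, read against programme length, would therefore reveal the arm of nearly every woman in the per-protocol set, even under a neutral arm code. As a percentage of scheduled sessions, both arms run from 50 to 100, and the count no longer gives the arm away.

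**5. How far the effect reaches.** Under Primary outcome, relative dose intensity is computed from medical records. Blinding (masking) says that the staff who prescribe, give and register chemotherapy are blinded to group. The recorded values therefore do not depend on the analyst's knowledge of arm, but the choices about how to analyse them do.

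**The case against.** The strongest reply is that the exception is disclosed. Allocation concealment mechanism names the ID holder by role, and Blinding (masking) mentions that person later, so a fair reader takes the sentence to mean nobody else. That stands as far as the premise goes, and one clause would repair it. It does not rescue the inference, which fails however many people know the IDs.

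A second reply is that coding of the group variable is commonly left to a statistical analysis plan, and none is at hand. This is right about silence, and silence alone would be no finding. But here the Protocol gives a mechanism and draws a conclusion from it, and that mechanism does not work. The open covariate list and choice of non-parametric test may also be settled in such a plan, and the 50% attendance threshold is already fixed.

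Three stronger readings are tempting and should be resisted:

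- *The analysis is unblinded.* The Protocol does not say who analyses the data, that the analyst sees labelled arms, or that the ID holder takes part.
- *The person who allocates also records the field tests after baseline.* This needs several sections read together, and the recording duty is stated without time points.
- *Field-test recording should move to someone else.* That person would need the IDs, which breaks the rule that only one member knows them. Disclosure of an ID to a team member also triggers the rule in Blinding (masking) that discards the participant's later data. The assessor, who openly knows the group and is the larger source of risk, would be unaffected.

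**Conclusion.** The point holds in limited form. The stated premise is contradicted within the Protocol, and the stated inference is invalid, so blinded analysis is unsupported by the mechanism offered. It is not shown to be impossible: if the ID holder stays out of the analysis and the arms are coded, the claim could be made true.

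No size can be put on any bias from what the Protocol gives. The exposure lies in covariate selection, test switching and exclusions, and these bear on the primary analysis as well as the secondary ones. A reader might infer that the relative dose intensity values themselves are compromised. The documents do not support that, provided the stated blinding of clinical staff holds.

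The conclusion assumes that the number in the quoted sentence is the participant's ID. That the holder also has the ID-to-arm list is a reasonable reading, but the verdict does not depend on it.

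**What to change.** Make four changes:

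1. In Blinding (masking), correct the sentence to name the ID holder, by role, as the exception, and stop deriving blinded analysis from concealment of IDs.
2. Release the analysis dataset with arms coded neutrally (X/Y) and attendance given as a percentage of scheduled sessions.
3. Have the ID holder keep the key and stay out of the analysis until the data are locked and covariates, exclusions and tests are fixed.
4. State plainly that field-test assessment after baseline is not masked to arm.

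Leave the recording of field-test results where it is. The cost is a recoded variable, a derived attendance percentage and one hand-over step before unblinding. No extra participants, visits or measurements are needed.
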